## **Study Protocol**

### ***Study design***

This parallel-group RCT was designed to compare retention days in residential treatment among participants randomly assigned to one of two study conditions as adjuncts to their residential SUD treatment: (1) MMWR and (2) Neurobiology of Addiction (NA), with the latter serving as the psychoeducational control condition. Baseline interviews occurred prior to randomization and post-intervention interviews occurred up to 14 days after the last class session of the study intervention. All participants received SUD treatment services as normally provided by the treatment facility without affecting the level of usual care provided to patients. The study site offered no structured mindfulness-based activities or services during the study period. The University of Southern California Institutional Review Board approved this study (UP-14-00391).

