Women's Treatment and Early Recovery (MBRP-W)

NCT02977988

June 02, 2021

Statistical Analysis Plan

Measures for data capture

Discharge Status. Following routine site protocol, the SUD site treatment team (i.e., certified SUD counselor, masters-level clinician therapist, and team supervisor masters-level therapist; the latter two registered with the Board of Behavioral Sciences) decided on a case-by- case basis if a client developed the necessary skills to complete residential treatment. One of three clinical progress designations was documented in a patient's chart at discharge based on their progress. *Completer:* patient completed course of treatment, met treatment goals and were sufficiently stable (i.e., developed sufficient coping skills, attended groups, adhered to requirements on days away from the facility such as calling in, returning on time and negative drug screen) to transition to stepped-down care. *Non-completer with satisfactory progress:* patient left treatment before completion of the treatment plan and be- fore achieving all treatment goals, but deemed by the clinical team as having made important progress toward treatment goals and improved stability. *Non-completer without satisfactory progress:* patient left treatment before completion of the treatment plan and the clinical team determined that little or no progress was made toward achieving treatment goals (i.e., left early in treatment without being able to re- ceive many services, administratively discharged due to multiple oc- casions of relapse as assessed by drug screens without changes in be- havior, repeatedly violated residential treatment rules such as bringing drugs on site). *In-residence:* patient remained in treatment at the residential treatment facility at the end of the analytic period (i.e., day 150). It was not possible to blind the discharge team to group assignment; however, the study was presented to the discharge team as a test of two alternative intervention approaches in an effort to prevent any unbalanced expectation of treatment benefit.

Days until discharge. We used site discharge records to calculate the number of days in residential treatment beginning from the study intervention start date (day 0) and ending at day 150. We selected an analytic time period to approximate the average length of stay at the SUD treatment site (5.5 months).

Data analysis

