Power analysis yielded an estimated sample size of 200 to 225 needed to detect a medium-sized effect (hazard ratio = 0.52 to 0.54) for residential treatment retention using a log-rank test with a two- sided 5% significance level and 80% power, given the probability of remaining in the treatment program in the control group is 50%. We conducted standard statistical diagnosis and performed descriptive analyses of background variables, assessed variable distributional properties, plotted means of the continuous outcome variables at each time point, and assessed internal consistency and test-retest reliability of study scales. We verified the adequacy of randomization on demo- graphic and clinical covariates, and identified variables found to differ between groups at $p < .20$ (Table 1) to include them as model covariates. Based on this criteria, the covariates included in all adjusted models were number of mental health diagnoses (i.e., SUD only, 1 co- morbid mental health dx, 2 + comorbid mental health dx), adulthood trauma exposure (LSC-R), PTSD diagnosis by DSM-5, and PTSD symptom score (PSS-SR), as well as a study design feature (i.e., days in residential treatment prior to study intervention start date obtained from clinic records) to account for exposure to residential treatment prior to the start of our study intervention.

To examine the differential risk of the outcome event (i.e., patient left treatment before completion of the treatment plan and made little or no progress toward achieving treatment goals based on clinical team determination), we applied Kaplan-Meier survival analysis using an intent-to-treat (ITT) approach with time starting on the first day of the study intervention and

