ending 150 days later. Participants with the discharge status of completer, non-completer with significant progress, and in-residence were coded as 1 for “retention”. Participants with the discharge status of non-completers without significant progress were coded as 0 for “non-retention”. Our examination of the survival curves revealed that group curves crossed at 50 days from the start of the intervention, which indicated the need for a piecewise model. Thus, a multivariable, 2-piece model (i.e., Piece 1 predicting outcome events during day 0 to 50 and Piece 2 predicting outcome events for days 51 to 150) was calculated. The first piece of the model coincided with the study intervention period and the second piece to the post-intervention period. Adjusted Cox proportional hazards regression (PROC PHREG), with days as the time scale, provide estimates of hazard ratios (HR) and the 95% confidence intervals (CI) for the non-retention outcome event. HR effect size estimates are categorized as small (0.77), medium (0.53), and large (0.36) (Amaro et al., 2016). We conducted logistic regression (PROC LOGISTIC) to test for group differences in satisfactory progress among the subgroup of non-completers. We used general linear mixed models (PROC MIXED) to examine differential changes in the self-reported mechanism of action variables from pre-intervention to post-intervention by group, adjusting for covariates. We used Pearson r to test for correlation between class attendance (as a dosage variable) and change in mechanisms of action measure scores. Pearson r effect sizes are small (.10), moderate (0.30), or large (0.50). All analyses were conducted in SAS version 9.4 (SAS Institute). All models used a maximum likelihood estimated approach to account for missingness.

Substance Use and Relapse

To quantify substance use at the three assessment points (baseline, postintervention, and follow-up), our trained study staff used the TLFB measure, which is a comprehensive retrospective calendar-based validated semistructured interview measure of daily substance use (29). From TLFB data, we calculated substance use from study intervention start date

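### The SAP's retention event is early departure without progress, so no stated analysis compares the retention days that the protocol names

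*SAP*

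**What the plan says.** The protocol (Study design) gives the purpose: "This parallel-group RCT was designed to compare retention days in residential treatment". The SAP (Measures for data capture, Days until discharge) builds a matching variable. It used site records to "calculate the number of days in residential treatment beginning from the study intervention start date (day 0) and ending at day 150".

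The same part of the SAP (Discharge Status) defines the category at issue, in which progress was rated satisfactory although the woman did not complete: "patient left treatment before completion of the treatment plan and be- fore achieving all treatment goals, but deemed by the clinical team". The definition then requires that the team saw important progress. It also says that the discharge team could not be blinded to group.

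The first Data analysis section then sets the survival event: "patient left treatment before completion of the treatment plan and made little or no progress toward achieving treatment goals", as determined by the clinical team. The coding follows: "Participants with the discharge status of completer, non-completer with significant progress, and in-residence were coded as 1" for retention, and "Participants with the discharge status of non-completers without significant progress were coded as 0" for non-retention. The adjusted Cox model reports hazard ratios for non-retention. A separate logistic model compares satisfactory progress among non-completers only.

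The SAP writes satisfactory progress in one place and significant progress in the other. I take these to be one category.

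**The concern.** A woman who walks out before finishing her plan has not been retained in the ordinary sense of the word, yet the coding counts her as retained if staff judged that she had progressed. The event therefore combines two things, whether she left early and how staff rated her at that point. An arm can do better on the second with no difference in the first.

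Two features make this matter more. The rating comes from people who could know the assigned group, whereas a discharge date needs no rating. And the SAP does not say whether a leaver with progress is censored on her discharge day or carried forward event-free to day 150. If she is censored, the censoring depends on progress and is unlikely to be non-informative.

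What is at stake is the wording of the main conclusion. A result on this event supports a statement about unsuccessful departure. It does not by itself support a statement that women stayed longer.

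**Working it through.** **1. Discharge outcomes against the two definitions**

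| Discharge outcome by day 150 | Left before completing the plan? | SAP coding |
|---|---|---|
| Completer | No | Retention |
| Non-completer with progress | Yes | Retention |
| Non-completer without progress | Yes | Non-retention (event) |
| In residence | No | Retention |

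The second row is the mismatch. Completers discharged before day 150 also have fewer days in residence while being coded as retained, but completion is not dropout.

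**2. The plan's own sample size**

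Inputs from the SAP's first Data analysis section: HR 0.52 to 0.54, two-sided 5%, 80% power, 50% of controls remaining, N = 200 to 225. I assume 1:1 allocation. Freedman's formula gives events d = (1.96 + 0.84)² × [(1 + HR)/(1 − HR)]², and N = d / mean event probability, with survival 0.50 in control and 0.50^HR in MMWR.

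- HR 0.52: d = 79; MMWR survival 0.697; mean event probability 0.401; N = 197.
- HR 0.54: d = 88; MMWR survival 0.688; mean event probability 0.406; N = 217.

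This is close to the stated 200 to 225. The sample size arithmetic is not the fault.

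**3. An illustration with no difference in early departure**

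The shares are assumed; the documents give none. Take 100 women per arm. In each arm 60 leave early, at the same times. Control: 35 without and 25 with progress. MMWR: 25 without and 35 with. If those 60 leave at a constant rate and nobody else leaves before day 150, mean days in residence are 150 × 0.60 / −ln(0.40) = 90 / 0.916 = 98 in both arms.

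- Leavers with progress censored at discharge: HR = 25/35 = 0.714.
- Leavers with progress carried to day 150: ratio of cumulative hazards at day 150 = ln(0.75)/ln(0.65) = 0.288/0.431 = 0.668.

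Approximate standard error of the log HR: √(1/25 + 1/35) = 0.262.

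- 0.714: 95% CI = exp(−0.336 ± 1.96 × 0.262) = 0.43 to 1.19; p about 0.20.
- 0.668: 95% CI = exp(−0.403 ± 1.96 × 0.262) = 0.40 to 1.12; p about 0.12.

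On the SAP's effect scale (small 0.77, medium 0.53) both lie between small and medium. They are averages over 150 days, not the SAP's two-piece estimates.

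**4. Range over other assumed shares**

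With identical early leaving and censoring at discharge, HR = (1 − share with progress in MMWR) / (1 − share with progress in control).

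| Share of leavers with progress, control | MMWR | HR |
|---|---|---|
| 40% | 50% | 0.50/0.60 = 0.83 |
| 30% | 50% | 0.50/0.70 = 0.71 |
| 20% | 50% | 0.50/0.80 = 0.62 |
| 30% | 20% | 0.80/0.70 = 1.14 |

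The last row shows that the rating can also push the estimate above 1.

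**5. What the logistic model would show**

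In the step 3 example the odds ratio for progress among non-completers is (35/25)/(25/35) = 1.96, unadjusted chi-square p about 0.07. That points to a difference in rating. But the model is restricted to women who left early, a group defined after randomization, and it takes no account of when they left. It cannot say whether early departure or days in residence differed.

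**The case against.** The best defence is that nothing is concealed. The SAP spells out the event and ties the hazard ratio to it. Staff decided case by case when a woman had the skills to complete, so discharge is partly a success and more days are not always better. The protocol text never defines retention days operationally, and separating unsuccessful from partly successful departure has clinical meaning. All of this stands. It supports keeping the event, but not letting it alone carry a claim about retention.

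The logistic model is a real mitigation, because it addresses the case where only the label differs. It is partial for the reasons in step 5. Days are also the time scale of the Cox model, but the departure of a woman with progress is never an event in it.

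Replacing the main event now would be hard to defend. The SAP reports that the survival curves had been examined, so a new main event would be chosen post hoc. Comparing mean days alone would also penalise an arm whose women complete sooner. Both objections are accepted and shape the fix.

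Three stronger readings are tempting, and the documents support none of them.

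- *A reported retention effect is spurious.* The example uses assumed shares, and neither of its hazard ratios reaches the 5% level at 100 per arm.
- *The event was picked to favour MMWR.* The SAP ties the look at the curves to the piecewise model, not to the choice of event.
- *The trial is underpowered.* If the 50% remaining counts every early leaver as lost, and a share of them in both arms is recoded as retained, Freedman power at N = 200 and HR 0.52 falls from 81% to 77% at a 10% share, 66% at 30% and 52% at 50%. But the SAP does not say whether the 50% already treats leavers with progress as remaining. If it does, nothing is lost.

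**Conclusion.** The concern holds as a mismatch between the outcome the protocol names and the event the SAP analyses. The mismatch itself follows from the text and needs no assumption. Its numerical size is unknown, because the share of early leavers rated as having progressed is not given for either arm. With equal early departure and the shares assumed above, a label-only difference gives hazard ratios of 0.62 to 0.83 when MMWR leavers are rated more favourably, and above 1 when they are rated less favourably. These figures rest on identical departure times and on a rating split that is constant over time.

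The main result can therefore be read as the hazard of departure without satisfactory progress. It cannot be read, without a further analysis, as evidence about days retained or about leaving early as such. The unblinded rating is a reason for caution. It is not evidence that ratings were biased.

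**What to change.** 1. Keep the present event, call it departure without satisfactory progress wherever retention or non-retention now appears, and limit its conclusion to that.
2. Alongside it, report by arm an analysis whose event is any departure before plan completion (both non-completer categories), with completion as a competing, successful exit and in-residence women censored at day 150. Label it supplementary, because the curves have already been examined.
3. Report days in residence to day 150 by arm as descriptive support, with a note that early completion shortens them.
4. State whether leavers with progress are censored at discharge or carried to day 150 in the present models.
5. Tabulate the discharge categories by arm, so that readers can see how much of any difference lies in leaving and how much in the rating.

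The discharge dates and statuses are already held, so no new data are needed. The cost is SAP wording plus modest extra analysis: a second event, competing-risk handling, and a check of whether the day-50 split is also needed for the new event. The retention result may prove less favourable than the present one.

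### The retention Cox model is cut at day 50 because the observed curves crossed there, which leaves the day 0–50 hazard ratio almost uninformative and the day 51–150 error rate unknown, and no overall between-arm test is named

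*SAP*

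**What the plan says.** The Protocol (Study design) gives retention days as the comparison the trial was built for. The SAP (Days until discharge) defines the outcome as the "number of days in residential treatment beginning from the study intervention start date (day 0) and ending at day 150".

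The power paragraph of the SAP's first Data analysis section derives 200 to 225 participants "for residential treatment retention using a log-rank test" (two-sided 5%, 80% power, HR 0.52 to 0.54), "given the probability of remaining in the treatment program in the control group is 50" per cent.

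The same section then applies Kaplan-Meier analysis over 150 days and reports that "group curves crossed at 50 days from the start of the intervention, which indicated the need for a piecewise model". A model with pieces at days 0–50 and 51–150 follows from that, and adjusted Cox regression is to "provide estimates of hazard ratios (HR) and the 95% confidence intervals (CI) for the non-retention outcome event". The SAP adds: "The first piece of the model coincided with the study intervention period and the second piece to the post-intervention period".

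On event coding: "Participants with the discharge status of completer, non-completer with significant progress, and in-residence were coded as 1", meaning retained. Only non-completers without significant progress count as events. On adjustment: "Based on this criteria, the covariates included in all adjusted models were number of mental health diagnoses", together with adult trauma exposure, PTSD diagnosis, PTSD symptom score and prior days in residence.

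For retention, the SAP gives no allowance in the test level or intervals for the choice of cut, no alternative cut, no exploratory label and no statement on other crossings. The log-rank test appears only in the power paragraph.

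**The concern.** The cut was chosen by looking at the outcome by arm, and the model was then fitted to the same data as if the cut had been fixed beforehand. This has three consequences.

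- **First piece.** Two survival curves that meet at day 50 have accumulated about the same hazard by then. An HR over days 0–50 is therefore pulled to 1 by the choice of cut, whatever happened inside the interval. Because the SAP equates this piece with the intervention period, a null result invites the reading that the arms did not differ during the intervention.
- **Second piece.** If the curves did not meet again after day 50, the data have been selected for one-sided separation from that day on, and a nominal 5% test rejects too often. If they did meet again, the selection works the other way.
- **Overall comparison.** The comparison on which the trial was sized has no named test or estimate in the analysis text, so a reader may be left with only the two pieces.

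**Working it through.** **1. Sizing reproduced.** Inputs from the power paragraph: control retention 50% (taken as the day-150 value), HR 0.52 to 0.54, two-sided 5%, 80% power. Assumed: 1:1 allocation.

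- Mean event probability at HR 0.52: [0.50 + (1 − 0.5^0.52)]/2 = (0.50 + 0.303)/2 = 0.401. At HR 0.54 it is 0.406.
- Freedman events, (1.96 + 0.84)² × [(1 + HR)/(1 − HR)]²: 79 at HR 0.52, so N = 79/0.401 = 197; 88 at HR 0.54, so N = 217.
- Freedman power is 80.8% (N=200, HR 0.52) and 81.5% (N=225, HR 0.54).

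The stated sizing is sound as a calculation for one overall log-rank test.

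**2. Power by piece under the planned constant HR.** Schoenfeld: power = Φ(√d/2 × |ln HR| − 1.96), with HR 0.52 and N=200.

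- Overall: d = 200 × 0.401 = 80.3, giving Φ(0.97) = 83%.
- Days 0–50: event probabilities 1 − 0.5^(1/3) = 0.206 and 1 − 0.5^(0.52/3) = 0.113, so d = 32.0 and power is 46%.
- Days 51–150: d = 80.3 − 32.0 = 48.3 and power is 62%.

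With HR 0.54 and N=225 the figures are 84%, 46% and 63%.

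**3. First piece.** Since S(t) = exp(−Λ(t)), equal S(50) in the arms means equal Λ(50), and a single HR over the interval is close to the ratio of these, which is 1. Simulation check: 100 per arm, constant hazard, observed crossing on days 45–55.

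- Null, unadjusted, cut at the crossing: 0 rejections in 11,327 trials. The standard deviation of the test statistic was 0.18 instead of 1.
- True HR 0.53 throughout: 0 of 2,296. A cut fixed at day 50 in advance rejects in 42%.
- Null, adjusted: 0 of 1,500 with one prognostic covariate (log-HR 0.5 per SD, arms imbalanced at p < .20). With all five SAP covariates it was 0.1–1.1% (assumed correlation 0.3, log-HR 0.3 per SD, the first four 0.2 SD apart between arms). The median adjusted HR was 1.0 if the imbalances pointed in random directions and about 0.8 if they aligned.
- True early harm, adjusted, day 50 the last crossing: with HR 2.0 to day 21 then 0.5, the first piece rejects in 0.7%; with HR 2.0 to day 42 then 0.5, in 3.1%.

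**4. Second piece under the null.** Events by day 150 were set at 25% or 50%. Because completers and those leaving with progress are not events, runs were made with and without early discharge as censoring.

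| Pattern around day 50 | Unadjusted | Adjusted |
|---|---|---|
| Curves cross again later | about 2–3% | not run |
| Any crossing near day 50 | about 5% | 4.3–4.9% |
| Last crossing | 8.5–14.4% | 8–11% |
| Only crossing | 8.4–15.9% | 8.1–10.6% |

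The adjusted figure for any crossing uses one covariate. Knowing only that day 50 was the first crossing does not settle the matter, because that group mixes trials that cross again with trials that do not.

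**5. Timing.** The Protocol (both Interventions descriptions) and the SAP (Substance Use and Relapse) give a 6-week intervention: 6 × 7 = 42 days, not 50. Under the planned HR of 0.52, days 43–50 hold 4.7 of 80.3 events.

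**6. Does a 6-week cut cure it?** No. Among unadjusted null data sets selected for a crossing on days 45–55, re-cutting at day 42 gives 0–0.3% for the first piece and 12.4–16.7% for the second if that crossing was the last.

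**The case against.** Crossing curves suggest non-proportional hazards, so a model with a time-varying effect is a reasonable response, and the SAP is open about why it cut where it did. Both points stand. They support looking at effects by period, but not nominal intervals around a cut placed exactly where the observed arms meet.

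The SAP also ties the first piece to the intervention, and its substance-use analysis uses a during/after split. That is a partial rationale independent of outcome. But the crossing is the reason given for the model, and day 50 is not six weeks. With about 5 of 80 events in the gap, the mismatch is minor.

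Covariate adjustment loosens the constraint on the first piece. It can shift the HR, but rejection stayed at about 0–1% under the null.

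Two stronger readings are tempting. A reader might infer that the day 51–150 false-positive rate is two to three times nominal. The documents do not support that: it would require that the curves did not cross again, which is not stated, and even then the adjusted model that the SAP specifies reached only about 11% under the assumed covariate effects. A reader might also infer that the log-rank test was dropped. The SAP applies Kaplan-Meier analysis over the whole 150 days, and a log-rank test may have accompanied it. The text supports only that no overall test is named.

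**Conclusion.** The concern holds in this form. The day-50 cut comes from the observed curves by arm and no allowance is made for it. The first-piece HR then has almost no ability to show early benefit or harm; this was stable across every null setting tried. The second-piece error rate cannot be fixed from the documents: it may lie below 5%, near it, or at about 8–16% unadjusted (about 8–11% adjusted), depending on later crossings. The stated 80% power belongs to an overall test that the retention analysis does not name, and not to either piece. The power split describes the plan, not the observed data: under a constant HR of 0.52 a last crossing on days 45–55 occurs in only 1.2–2.0% of trials.

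The figures assume 1:1 allocation, constant hazards unless stated, and 100 per arm; the analysed N of 200 is stated only in the substance-use section. The adjusted figures also rest on assumed covariate effects. This should be corrected, because it bears on the trial's main comparison and the correction is cheap.

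**What to change.** 1. Report the overall day 0–150 log-rank test, with the adjusted overall Cox HR, as the main retention result.
2. Label the day 0–50 and 51–150 HRs post hoc and exploratory.
3. State whether the curves crossed again after day 50, and whether they crossed before it.
4. State that a null day 0–50 HR cannot be read as no difference during the intervention.
5. Correct the statement that the first piece coincided with the intervention period.
6. Beside the overall result, show an exploratory treatment-by-period result, for example with a 6-week split to match the during/after split of the substance-use analysis. It needs the same exploratory label and the same first-piece warning.

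The cost is SAP wording and a re-run of existing models on existing data. There is a real downside: if hazards truly reverse, a single HR is hard to interpret and the overall log-rank test is weak. Its power is 24% with HR 2.0 to day 21 then 0.5 (day-42 interaction 59%), and 5.5% with HR 2.0 to day 42 then 0.5 (interaction 91%). That is why item 6 belongs next to item 1. The headline may also be less favourable than the day 51–150 HR alone.

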### *Interventions*

#### ***Moment-by-Moment in Women's recovery (MMWR)***

This intervention was delivered twice weekly for 80 min each for a total of 12 group sessions (6 weeks) during residential treatment. MMWR was guided by an instructional manual with

standardized lesson plans. An experienced teacher trained in both MBSR and MMWR facilitated all sessions along with an on-site masters-level clinician with experience in SUDs who co-facilitated the intervention. Each class session had a central theme divided into five segments in the following general order: (1) welcome, review of group culture, brief homework practice check-in, objectives, and brief mindfulness meditation or practice; (2) didactic psychoeducational presentation and discussion of lesson content; 3) experiential meditation and mindfulness practices related to the session's theme; (4) practice of sitting or walking meditation, body scan, and/or standing stretching; and (5) selected reading related to session topic, assignments for the next class, and closing meditation. Trainees were expected to learn skills to approach experiences and stressors using mindfulness principles. Students learned about the role of automatic reactivity to stressors and its relation to addiction and relapse; the connections between stress, triggers, and relapse; and how to use mindfulness practices to respond best to related thoughts, emotions, body sensations (including those related to stress in a residential treatment setting that could lead to treatment dropout), and triggers while still avoiding relapse. As with MBSR, trainees learned and practiced self-regulation strategies using four foundational mindfulness practices. Teachers instructed on the use of formal (audio- guided sitting meditation, sitting meditation without audio, loving kindness meditation, walking meditation, body scan, and mindful stretching) and informal practices (stop light technique, triangle of awareness, mindfulness of breath, mindfulness of emotions, mind- fulness of thoughts, mindfulness of body sensations, and mindfulness of cravings). Throughout the course, students were encouraged to bring mindful awareness into their daily activities by using informal practices and to engage in formal meditation practices as homework in accordance with practice assignments and guided meditation audio recordings. Participants received a MMWR Participant Workbook at the beginning of the course organized by session, containing key concepts and practices introduced in each session, and homework and practice assignments for each session. Participants were asked to bring their Workbook to each session so that they

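### The additional logistic regression of satisfactory progress among non-completers conditions on a post-randomisation outcome, so its odds ratio is not a randomised comparison and can be biased either way

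*SAP*

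**What the plan says.** The SAP's first Data analysis section (retention) contains one sentence on this model: "We conducted logistic regression (PROC LOGISTIC) to test for group differences in satisfactory progress among the subgroup of non-completers". It gives no rationale, estimand, sensitivity analysis or caution on interpretation, and does not say whether the model is adjusted.

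Status is defined in the SAP under Discharge Status: "One of three clinical progress designations was documented in a patient's chart at discharge based on their progress". A completer is the best of the three: "patient completed course of treatment, met treatment goals and were sufficiently stable". The two non-completer categories differ by whether the clinical team judged progress satisfactory. Women still in the facility at day 150 are listed as a separate fourth status, so the natural reading is that they, like completers, fall outside the logistic model. Of those who assign the status, the SAP says: "It was not possible to blind the discharge team to group assignment".

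The main retention analysis is built differently. "Participants with the discharge status of completer, non-completer with significant progress, and in-residence were coded as 1", meaning retained, and "Participants with the discharge status of non-completers without significant progress were coded as 0", meaning not retained. (The coding sentences say significant where the definitions say satisfactory; I take these to be the same category.) All four statuses enter that analysis.

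**The concern.** Randomisation makes the arms comparable as whole groups. It does not make comparable the part of each arm that later failed to complete, if assignment affects who fails to complete. Here it is meant to. The protocol's Study design section makes days retained in treatment the comparison of interest, and the MMWR section says that participants learn to respond to "stress in a residential treatment setting that could lead to treatment dropout". If MMWR works, some women who would have left early complete or stay, and so drop out of the MMWR side of the logistic model. Those who remain are a differently selected group from the control non-completers.

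Baseline covariates cannot be relied on to repair this, because the selection also depends on unmeasured factors.

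At stake is how this one odds ratio is read. The SAP presents it as a test of group differences, so a reader would take it as a treatment effect on progress.

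**Working it through.** **Notation.** As proportions of a whole arm (0 = control, 1 = MMWR), let U = left without satisfactory progress, S = left with satisfactory progress, C = completed or in residence, with U + S + C = 1.

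**Inputs from the SAP (first Data analysis section).** Control probability of remaining 50%; hazard ratio 0.52 to 0.54; the design is stated as "using a log-rank test with a two- sided 5% significance level and 80% power"; N = 200 to 225.

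**Assumptions.** Remaining means free of the non-retention event, so U0 = 0.50. Allocation is 1:1, 100 per arm. S0 is not given and is varied from 0.10 to 0.30. Status is treated as fixed proportions at day 150.

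**Step 1: the plan's own sample size.** Freedman events = (1.960 + 0.842)² × [(1 + HR)/(1 − HR)]². N = events / mean event probability, with MMWR retention 0.50^HR.
- HR 0.52: 79 events; MMWR retention 0.697; mean event probability 0.401; N = 197.
- HR 0.54: 88 events; MMWR retention 0.688; mean event probability 0.406; N = 217.

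The first is close to 200; the second is 3.6% below 225. Power by the same method is 80.8% at N = 200 with HR 0.52, and 81.5% at N = 225 with HR 0.54. The planning values are coherent enough to use. The conclusion below does not depend on matching N exactly.

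**Step 2: the planned benefit with every woman counted.** At HR 0.53, U1 = 1 − 0.50^0.53 = 0.307. The odds ratio for avoiding the event is (0.693/0.307)/(0.50/0.50) = 2.25, however the other women divide between S and C.

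**Step 3: the odds ratio among non-completers.** This is

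(S1/U1)/(S0/U0) = (S1/S0)/(U1/U0), with U1/U0 = 0.307/0.50 = 0.615.

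It therefore depends on what happens to S, which the planned effect leaves open. In every row below the whole-arm odds ratio is 2.25 and no woman does worse under MMWR.

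| Where women move under MMWR | S1 | OR, S0 = 0.10 | OR, S0 = 0.20 | OR, S0 = 0.30 |
|---|---|---|---|---|
| Avoided events go to C; half of S also moves to C | S0/2 | 0.81 | 0.81 | 0.81 |
| S shrinks in the same proportion as U | 0.615 × S0 | 1.00 | 1.00 | 1.00 |
| Uniform shift on a latent normal progress scale | 0.094, 0.201, 0.325 | 1.53 | 1.63 | 1.76 |
| Avoided events go to C; S unchanged | S0 | 1.63 | 1.63 | 1.63 |
| Avoided events go to S; all of the original S moves to C | 0.193 | 3.13 | 1.57 | 1.04 |
| Avoided events go to S; half of the original S moves to C | S0/2 + 0.193 | 3.94 | 2.38 | 1.86 |
| Avoided events go to S; nothing else moves | S0 + 0.193 | 4.76 | 3.19 | 2.67 |

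The result falls below 1 only if S1/S0 is below 0.615, that is, if the with-progress leavers shrink proportionally more than the without-progress leavers. The range 0.81 to 4.76 covers the paths tried; it is not a mathematical bound.

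**Step 4: precision.** With 100 per arm and a non-completer odds ratio of 1, the 95% confidence interval would be about 0.33 to 3.01 (S0 = 0.10), 0.43 to 2.32 (S0 = 0.20) or 0.48 to 2.08 (S0 = 0.30).

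**The case against.** The strongest reply is that this is one sentence about an additional analysis. The main retention analysis already contrasts unsatisfactory discharge with everything else and keeps completers and in-residence women in. The power calculation and the intention-to-treat label belong to that analysis, and nothing calls the logistic result causal. How leavers left is a fair descriptive question. All of this stands, and it limits the reach of the point. It does not rescue the test. The main analysis merges left with progress, completed and in residence into one retained category, so it neither supplies nor corrects the contrast that the logistic model attempts.

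A reader might infer that a real benefit will show up here as no effect or as harm. The documents do not support that. It can be constructed: with a control split of 35/35/30 per 100 (U/S/C), moving 10 women from S to C gives (25/35)/(35/35) = 0.71. But that needs no effect at all on the trial's own event, the split is invented, and the 95% confidence interval is about 0.36 to 1.43. Under a common odds ratio of 2.0 the same split becomes 21.2/32.6/46.2, and the non-completer odds ratio is (32.6/21.2)/(35/35) = 1.54, in the direction of the benefit. Other paths exaggerate it.

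A whole-sample model also brings choices of its own. The SAP does not rank in-residence women against completers. The protocol allows stays of up to 12 months, so these women have no final discharge status at day 150. The second Data Analysis section leaves 25 randomised women out of its N = 200, and the documents do not confirm that their day-150 status is on file. These objections stand and shape the fix.

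In simulations with that 35/35/30 split, 100 per arm and a common odds ratio of 2.0, the subgroup test has about 21 to 22% power and a three-level rank test in all women about 75%. The two tests answer different questions, so the gap is not power recovered for one estimand.

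**Conclusion.** The point holds for this additional model only. Its odds ratio compares groups selected by an outcome that MMWR is meant to change, so it should not be read as a treatment effect. For one planned benefit, worth 2.25 in the whole arm, it ranges from about 0.81 to 4.76 across plausible movements between statuses. Confidence is high in the mechanism but not in the direction or size of the bias, which cannot be known without the split among statuses. The figures rest on reading 50% remaining as 50% event-free, on 1:1 allocation and on S0 between 0.10 and 0.30.

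A reader might also infer that the retention conclusion is at risk. It is not on this ground: the Kaplan-Meier and Cox analysis uses all four statuses and does not condition on completion. The unblinded designation bears on any analysis of discharge status and is a separate matter.

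**What to change.** 1. In the first Data analysis section, replace the logistic test by a descriptive table of the non-completer split by arm, shown with the counts of completers and in-residence women. Attach no treatment-effect test or claim to it.
2. Make any inferential comparison of discharge status in the whole intention-to-treat sample with available discharge records, and state how many randomised women lack a record, by arm. One suitable model is proportional odds (PROC LOGISTIC) on left without satisfactory progress < left with satisfactory progress < completed or in residence at day 150, with the covariates that the SAP lists for its adjusted models.
3. Check the proportional-odds assumption, and run a sensitivity analysis on where in-residence women are placed.

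The cost is a change of SAP wording and one re-run on discharge status that the site already records. The downside is small: an assumed ordering of categories and the proportional-odds assumption. The ordinal model also ignores timing, which the retention analysis covers. If no replacement model is wanted, step 1 alone removes the misleading test.
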